#### **Definitions**

##### **1.1 Pre-existing condition**

A pre-existing condition is one that is present prior to randomization. A worsening of a pre-existing condition after taking the first dose of investigational product should be reported as an AE.

##### **1.2 Adverse Event (AE)**

An AE is defined as any unfavorable and unintended sign (including a clinically meaningful abnormal laboratory finding), symptom, or disease temporally associated with the use of an investigational product, whether or not related to the investigational product.

A medical procedure is not considered and should not be reported as an AE. However, the medical condition which led to the procedure should be considered as an AE and be reported as such.

##### **1.3 Related Adverse Event**

A related AE is one where, according to the Investigator, there is a reasonable possibility that the event may have been caused by the study product.

##### **1.4 Serious Adverse Event (SAE)**

Serious Adverse Events (SAE) are those that meet any of the following International Council for Harmonisation (ICH) criteria:

- Is fatal or immediately life-threatening (NOTE: the term "Life-Threatening" refers to an event in which the patient was at immediate risk of death at the time of the event; it does not refer to an event which could hypothetically have caused death had it been more severe);
- Results in persistent or significant disability/incapacity;
- Requires or prolongs patient hospitalization;
- Is a congenital anomaly/birth defect in the offspring of the patient;
- Is a cancer;
- Is an overdose (intentional or accidental);
- Is judged to be medically important.

Medically important events may not be immediately life-threatening, result in death or hospitalization, but may jeopardize the patient or may require intervention to prevent one of the outcomes listed in the definition above. Serious adverse events are to be reported if they are known to occur within 21 days after randomization.

Medical and scientific judgment should be exercised in deciding whether other AEs meet these criteria and are immediately reportable to the sponsor or its designee.

Hospitalization is defined as a patient admission to a hospital for medical treatment or observation; a visit to the emergency room for an outpatient consultation is not considered a hospitalization. Moreover, hospitalization for therapy of the target disease(s) of the study if the protocol explicitly anticipated and defined the symptoms or episodes is not considered SAEs.

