## **5 STUDY METHODOLOGY**

### **5.1 Efficacy Outcomes**

- The **primary endpoint**:  
Proportion of subjects with any of the following COVID-19 symptoms: fever, cough, shortness of breath or anosmia, at day 3, 7, 10 and 14.
- The **secondary endpoints**:
  - 1- Mean number of COVID-19 symptoms (range 0 – 13) at day 3, 7, 10 and 14.
  - 2- Duration of COVID-19 symptoms, defined as the number of days between first symptoms and complete disappearance of any symptom.
  - 3- For each COVID-19 symptom listed in the appendix, proportion of subjects with the symptom at day 3, 7, 10 and 14.

Duration of symptoms will be determined as follows:

- If randomization and study product reception by participant occur the same day, first day of symptoms will be defined as the day of randomization;
- If randomization and study product reception by participant occur on different days, first day of symptoms will be defined as the day of study product reception.

- The **exploratory endpoints**:
  - 1- For each COVID-19 symptom listed in the appendix, proportion of subjects with the symptom on a daily basis based on patients' diary.
  - 2- Composite of COVID-19-related hospitalization, mechanic ventilation or death in the 14 days following randomization.

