#### 5.2.1.1 Serious Adverse Events

Serious Adverse Events (SAE) are those that meet any of the following International Council for Harmonisation (ICH) criteria:

- Is fatal or immediately life-threatening;

- Results in persistent or significant disability/incapacity;
- Requires or prolongs inpatient hospitalization;
- Is a congenital anomaly/birth defect in the offspring of the patient;
- Is a cancer;
- Is an overdose (intentional or accidental);
- Is judged to be medically important.

Medically important events may not be immediately life-threatening or result in death or hospitalization but may jeopardize the patient or may require intervention to prevent one of the outcomes listed in the definition above. Serious Adverse Events are to be reported if they are known to occur within 14 days after randomization.

Medical and scientific judgment should be exercised in deciding whether other AEs meet these criteria and are immediately reportable to the sponsor or designee.

In the event of a serious or life-threatening adverse event, or in the event of death, immediately report the event on the appropriate SAE form in the eCRF.

**FOR ANY SAFETY QUESTIONS OR CONCERNS, PLEASE CONTACT:  
MHICC Medical Monitor**

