#### **3.3 Hospitalization or Surgery/Procedure**

Any AE that results in hospitalization (admitted and not just an emergency room visit) should be reported as an SAE. Any condition/diagnosis responsible for surgery/procedure should be reported as an AE if it meets the criteria for an AE. A medical procedure is not considered and should not be reported as an AE. The surgery/procedure itself will be reported as a Clinical Outcome of the underlying event. Events that prolong any hospitalization are reported as SAEs.

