#### 4.3 Tertiary (or Exploratory) Efficacy Endpoints

- For each of the 13 COVID-19 symptoms listed in the appendix, proportion of subjects with the symptom on a daily basis based on patient's diary. Presence of these symptoms (Yes/No) will be identified using the Covid-19 Symptoms Form of the eCRF (variables COUGH, FEVER [considered a symptom if greater than 38°], FEVERISH, STHROAT, ..., ANOS) at DAY 1 to DAY 14.
- Composite of COVID-19-related hospitalization, mechanic ventilation or death in the 14 days following randomization. These events will be identified using the Adverse Events Form of the CRF:
  - ✓ COVID-19 related hospitalization: AECOVID=YES and AESER=YES and AESHOSP=YES; date of hospitalization = ADMDAT
  - ✓ COVID-19 related mechanic ventilation: AECOVID=YES and AEVENT=YES; date of mechanic ventilation = AEVSDTA
  - ✓ COVID-19 death: AECOVID=YES and AEOUT=Fatal; date of death = AEENDAT1

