### 5.2 Serious Adverse Events

Serious Adverse Events (SAE) are those that meet any of the following International Council for Harmonisation (ICH) criteria:

- Is fatal or immediately life-threatening (NOTE: the term "Life-Threatening" refers to an event in which the patient was at immediate risk of death at the time of the event; it does not refer to an event which could hypothetically have caused death had it been more severe);
- Results in persistent or significant disability/incapacity;
- Requires or prolongs patient hospitalization;
- Is a congenital anomaly/birth defect in the offspring of the patient;
- Is a cancer;
- Is an overdose (intentional or accidental);
- Is judged to be medically important.

Medically important events may not be immediately life-threatening, result in death or hospitalization, but may jeopardize the patient or may require intervention to prevent one of the outcomes listed in the definition above. Serious adverse events are to be reported if they are known to occur within 21 days after randomization.

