#### 6.4.3 Exploratory Analysis

- The number and proportion of subjects with each individual COVID-19 symptom will be summarized on a daily basis, i.e. at 1, 2, 3, ..., 14 days, overall and by treatment group.
- In each treatment group, the incidence of the composite of COVID-19-related hospitalization, mechanic ventilation or death in the 14 days following randomization will be calculated as the number of subjects who either died, were hospitalized or required mechanic ventilation in the 14 days following randomization, divided by the number of subjects randomized to that treatment group. Number and proportion of subjects with this composite endpoint will be presented, overall and by treatment group. The incidence will be compared between treatment groups using a chi-square test. If the number of events is low, Fisher's exact test could be used.

Since this endpoint is defined in the 14 days following randomization, the delay between an event and randomization will be calculated as date of the event (date of death, date of hospitalization or date of mechanic ventilation) – date of randomization (in days), and any event for which the delay is > 14 days will be excluded from the analysis. In case the date of the event is incomplete (the exact day could be unknown, but the month and year should be known as

they are required fields), the missing event will be assumed to occur the first day of the month, unless the randomization date is after, in which case the event will be assumed to occur the day of the randomization.

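### SAP 4.3 counts a COVID-19 admission in the composite only if it is flagged serious, but the protocol conflicts on whether such an admission is an SAE

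*Protocol*

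**What the plan says.** Protocol Appendix B 1.4 lists hospitalization among the SAE criteria and then ends with an exemption: "hospitalization for therapy of the target disease(s) of the study if the protocol explicitly anticipated and defined the symptoms or episodes is not considered SAEs". Appendix B 3.3 has no exemption: "Any AE that results in hospitalization (admitted and not just an emergency room visit) should be reported as an SAE". The SAE criteria in Protocol 5.2.1.1 ("Requires or prolongs inpatient hospitalization") and in SAP 5.2 ("Requires or prolongs patient hospitalization") have none either.

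Protocol 5.1 defines the second exploratory endpoint as "Composite of COVID-19-related hospitalization, mechanic ventilation or death in the 14 days following randomization". SAP 4.3 derives its parts from the adverse event form:

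- Admission: "COVID-19 related hospitalization: AECOVID=YES and AESER=YES and AESHOSP=YES".
- Ventilation: "COVID-19 related mechanic ventilation: AECOVID=YES and AEVENT=YES".
- Death: AECOVID=YES with a fatal outcome.

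Only the admission rule uses AESER. SAP 6.4.3 describes the numerator as "the number of subjects who either died, were hospitalized or required mechanic ventilation in the 14 days following randomization" and does not mention seriousness.

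**The concern.** An efficacy component depends on a safety-reporting flag, and the documents disagree on how to set that flag for the very event being counted. COVID-19 is the target disease. Its symptoms are itemised in the diary, and admission for it is a named endpoint, so a reporter could reasonably conclude that the exemption in Appendix B 1.4 applies. A second reporter who reads Appendix B 3.3 or Protocol 5.2.1.1 would flag the same admission as serious.

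The composite is the trial's only efficacy endpoint on severe outcomes. Few events can be expected among outpatients, so losing a handful could empty it. The same flag decides what appears in SAE Tables 3.2.3 and 3.2.4 and in Listing 8.

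**Working it through.** The point rests mainly on comparing the text. The plan gives no expected rate for the composite, so there is no plan figure to reproduce. The only planning number used below is the arm size: 91 / (1 - 0.15) = 107.06, rounded up to 108 per arm, or 216 in total, as in Protocol 8.1.

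**Step 1. The rules for a COVID-19 admission**

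| Place | Is it an SAE? |
|---|---|
| Protocol Appendix B 1.4 | No, if the protocol explicitly foresaw and defined the symptoms or episodes |
| Protocol Appendix B 3.3 | Yes, no exception |
| Protocol 5.2.1.1 | Yes, no exception |
| SAP 5.2 | Yes, no exception |

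Whether the condition in 1.4 is met is open, because the protocol never says which admissions are exempt. No passage ranks 1.4 against 3.3. The precedence clause in SAP section 1 does not help. It settles differences between SAP and protocol text, whereas this conflict lies inside the protocol, and the clause does not change a flag already entered in the eCRF.

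**Step 2. What AESER=YES does under each rule**

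- If every admission is an SAE, AESER=YES always accompanies an admission and the condition is redundant.
- If the exemption is applied, an admission that meets no other SAE criterion carries AESER=NO and is not counted.
- If reporters differ, some are counted and some are not.

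The condition therefore never improves the derivation. It either does nothing or removes true events.

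**Step 3. Who is exposed**

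A subject who is also ventilated or dies still enters the composite, because those components do not use AESER. An admission that meets another SAE criterion, such as being life-threatening, is still flagged. What remains is the non-fatal, non-ventilated admission with no other SAE criterion. It would stay in the AE listing and, if treatment-emergent, in the AE tables.

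**Step 4. Size, under an assumed admission rate of 1% to 5%**

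- Whole trial: 216 x 0.01 = 2.2; 216 x 0.05 = 10.8.
- Per arm: 108 x 0.01 = 1.1; 108 x 0.05 = 5.4.

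Illustration for one arm with 5 such admissions and no ventilation or death, with exact (Clopper-Pearson) 95% limits:

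- All counted: 5/108 = 4.6%, interval 1.5% to 10.5%.
- None counted: 0/108, upper limit 1 - 0.025^(1/108) = 3.4%.

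**Step 5. Partial loss**

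Let r be an assumed composite rate, q the share of events that are admission only, and s the share of those entered as AESER=NO. Events counted = 216 x r x (1 - q x s).

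| r | True events | Counted, s = 0.5, q from 1.0 to 0.6 | Counted, s = 1, q from 1.0 to 0.6 |
|---|---|---|---|
| 2% | 4.3 | 2.2 to 3.0 | 0 to 1.7 |
| 5% | 10.8 | 5.4 to 7.6 | 0 to 4.3 |

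**The case against.** The strongest reply is that the exemption is conditional and probably has no effect. Listing symptoms and naming an endpoint is not an explicit definition of exempt admissions, and every other passage makes hospitalization an SAE. SAP 4.3 was written from the annotated case report form and looks for these admissions among serious events, which suggests that its authors expected them to be flagged. On that reading the AESER condition is merely redundant. Appendix B 2.2 also sends SAE reporting to Protocol 5.2.1.1, which has no exemption.

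This makes the harmless reading plausible but does not establish it. Appendix B 2.2 covers how an SAE is reported, not what counts as one. The exemption remains in the current protocol for any reporter to apply.

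Several narrower points stand:

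- SAP 6.4.3 is shorthand (it also omits COVID-19 relatedness), so its silence on seriousness is weak evidence of a second rule.
- The eCRF is not among the documents. If the admission fields open only when AESER=YES, editing the algorithm alone recovers nothing.
- If 1.4 does govern, absence from the SAE tables is what it intends. That does not excuse absence from the composite, which Protocol 5.1 defines without reference to seriousness.
- Seriousness is judged under blinding, so there is no evident reason for the loss to favour an arm.
- The stake is descriptive. Even with full capture, Fisher's exact test gives p = 0.21 for 5 against 1 of 108 and p = 0.06 for 5 against 0.

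**Conclusion.** The concern holds. The protocol contradicts itself on the SAE status of a COVID-19 admission, and SAP 4.3 turns that contradiction into a possible undercount of the exploratory composite. The loss depends on the study team applying Appendix B 1.4, which the documents neither require nor rule out.

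The figure of about 2 to 11 admissions at risk rests wholly on the assumed 1-5% rate. The fall from 5/108 to 0/108 is a worst case for one arm. The weight is moderate: the effect is confined to one component of an exploratory endpoint and to the SAE summaries, but the correction is nearly free and should be made before lock.

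**What to change.** 1. Reconcile Protocol Appendix B 1.4 with Appendix B 3.3, Protocol 5.2.1.1 and SAP 5.2, and state which rule governs AESER for COVID-19 admissions.
2. In SAP 4.3, derive the component as AECOVID=YES with an admission recorded (AESHOSP=YES or ADMDAT present), without AESER. Check this against the eCRF.
3. Before lock, query every AECOVID=YES record for an admission. This covers the case where the admission fields open only for serious events. It is feasible because Appendix B 4.2 requires study endpoints to be entered in the eCRF in addition to SAEs.

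The cost is one protocol sentence, one line of the SAP algorithm and one data query. SAE counts may rise slightly if the reconciliation makes these admissions SAEs; removing AESER from the composite does not itself change them. After unblinding, the same change could look data-driven, so it needs to come earlier.

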### **1.5 Life-Threatening Adverse Event**

A life-threatening AE is an AE that, in the opinion of the investigator, places the patient at immediate risk of death from the reaction as it occurred.

### **1.6 Clinical Laboratory Adverse Event**

A clinical laboratory abnormality is regarded as an AE if it has been confirmed by at least 1 repeat test and suggests a disease and/or organ toxicity severe enough to require active management.

### **1.7 Treatment-Emergent Signs and Symptoms (TESS)**

A TESS event is any AE that was not present prior to randomization or that worsens in character, intensity or frequency while the patient is in an active treatment period.

### **1.8 Post-treatment Adverse Event**

A post-treatment AE is any AE that occurs after treatment is discontinued.

## **2 HANDLING OF ADVERSE EVENTS**

### **2.1 Treatment-Emergent Signs and Symptoms**

Any condition/diagnosis that meets the definition of a TESS event is captured adverse event from and kept in the patient's chart.

### **2.2 Serious Adverse Events**

All SAEs are to be immediately reported as outlined in Section 5.2.1.1., Serious Adverse Events, within 24 hours of the Investigator's first knowledge of the event.

### **2.3 Intensity**

The following criteria are used to assess the intensity of each AE:

- Mild: The patient is aware of the sign or symptom, but finds it easily tolerated.
- Moderate: The patient has enough discomfort to cause interference with or change in usual activities.
- Severe: The patient is incapacitated and unable to work or participate in many or all usual activities.

### **2.4 Relationship to Study Drug – Physician's Assessment**

Causal relationship between study drug and an AE will be reported by physician's assessment as follows: not related, possibly and probably.

### **2.5 Clinical Outcome**

The following categories are used to assess the clinical outcome of each AE:

- Recovered – The patient has fully recovered from the AE with or without observable residual effects.
- Not Yet Recovered – the patient is still being treated for the residual effects of the original AE. This does not include treatment for pre-existing conditions including the indication for the study drug.
- With sequela.
- Died Due to this Adverse Event
- Died, Other Causes
- Unknown
- Surgery/Procedure

### **3 CAPTURING AVDERSE EVENTS**

#### **3.1 Pre-Existing Condition**

A pre-existing condition should be captured in the medical history and kept in the patient's chart.

#### **3.2 Clinical Laboratory Adverse Event**

A clinical laboratory abnormality should be reported as an AE only if it is considered to be clinically significant by the investigator and confirmed by repeat testing.

#### **3.3 Hospitalization or Surgery/Procedure**

Any AE that results in hospitalization (admitted and not just an emergency room visit) should be reported as an SAE. Any condition/diagnosis responsible for surgery/procedure should be reported as an AE if it meets the criteria for an AE. A medical procedure is not considered and should not be reported as an AE. The surgery/procedure itself will be reported as a Clinical Outcome of the underlying event. Events that prolong any hospitalization are reported as SAEs.

#### **3.4 Death**

The cause of death should be reported as an AE.

### **4 REPORTING TO THE SPONSOR**

#### **4.1 Immediately Reportable Adverse Events**

If an AE meets the definition of Serious, it must be reported IMMEDIATELY in the eCRF. If the eCRF is not available, the investigator should send the paper SAE form by fax ([contact]) as soon as possible and within 24 hours of knowledge of the event. Upon return of the availability of the eCRF, the information written on the paper SAE form must be recorded in the eCRF. For any questions or concerns, the investigator may send an email to the MHICC Medical Monitor at **Hesperco\[contact]**. If any SAE occurs the investigator, at his discretion, can withdraw the patient from the study while taking the appropriate follow-up action.

MHICC Medical Monitor or his designated representative is responsible to report SUSARs to Regulatory Authorities and to notify Ingenew Pharma.

#### **4.2 Other Adverse Events**

Study endpoints are to be reported in the eCRF within 5 days of awareness of the event.

In addition to SAEs and study endpoints, the only AEs to be recorded on the eCRF are those that are judged related to the study medication by the investigator or that are laboratory abnormalities

judged clinically significant by the investigator. Information collected will include the onset, duration, severity, relationship to study drug, and the management.

#### **4.3 Follow-Up Period**

For SAEs, the patient must remain under observation until the SAE has subsided or stabilized and all serious findings have returned to normal or stabilized. Any follow-up information to an initial SAE report must be updated in the eCRF. Serious Adverse Events are to be reported if they are known to occur within 21 days of randomization.

## Appendix C      **Other Administrative and Regulatory Procedures**

This appendix provides information necessary to administer the study in compliance with global Good Clinical Practice (GCP) and government regulations.

Your signature on this cover page of the protocol, subsequent amendments, addenda, and the Clinical Trial Agreement confirms that:

- You have been given appropriate information on the study drug
- You have read and understand the protocol and appendices
- You agree to conduct the study in accordance with the provisions of the protocol and applicable regulations
- You acknowledge the sponsor's ownership of the data and results obtained from the conduct of the protocol
- You agree to maintain the confidentiality of information as outlined in this protocol

### **1. ADMINISTRATIVE PROCEDURES**

#### **1.1 Ethics and Informed Consent**

##### **1.1.1 Declaration of Helsinki**

This study will be conducted in accordance with the Declaration of Helsinki.

##### **1.1.2 Ethics Committee (EC) Review and Approval of the Study**

An EC that is organized and operates according to GCP and applicable laws and regulations, should safeguard the rights, safety, and well-being of all trial patients. No patient should be admitted to a trial before the EC issues its written approval/favorable opinion of the trial.

The investigator is responsible for:

- Promptly reporting to the EC all changes in the research activity, all unlabeled AEs, and all unanticipated problems involving risks to human patients or others;
- Not making any changes in the research without EC approval, except when absolutely necessary to eliminate apparent immediate hazards to human patients;
- Submitting a progress report describing the status of the clinical investigation to the EC at appropriate intervals not exceeding 1 year; and
- Submitting a final report when required by the EC within 3 months following completion, termination or discontinuation of the study. Copies of these reports will also be provided **to the sponsor or the sponsor's designated representative.**

In general, all communications with the EC regarding the study will be handled by the principal investigator or coordinating investigator, (if applicable) of the study. The sponsor or the sponsor's designated representative may directly contact the EC if necessary, but must not

attempt to influence the EC in any way. A copy of all communications from the EC to the investigator regarding its review of an initial approval of the study and its re-approvals at intervals must be provided to the sponsor by the investigator.

